9.1 Censoring Rules

9.1.1 Censoring rules for Symptomatic Skeletal Event-Free Survival (SSE-FS)

Comparison 1:

- Arm C subjects who had SSE assessments or SSE event or death (in the absence of an SSE event) after ‘pooling cut-off date’ will be censored on last SSE assessment date prior to ‘pooling cut-off date’. Refer to Section 4.5 for pooling cut-off date.
- All other subjects in arms A, B and C, refer to [Table 9–1](#) for censoring rules.
- Symptomatic Skeletal Event Free Survival (SSE-FS) following randomization = End Date – Date of Randomization +1

Table 9–1 Comparison 1: Censoring for Symptomatic Skeletal Event Free Survival (SSE-FS)

Situation	End Date	Censored	Reason for Censoring
No post-randomization SSE assessment and no death	Date of Randomization	Yes	No post-baseline SSE assessments and no death
Subject had a SSE event	Date of first SSE	No*	N/A
Death without prior SSE (<13 weeks between last SSE assessment and death) #	Date of Death	No*	N/A
Death without prior SSE (≥ 13 weeks between last SSE assessment and death) #	Last SSE assessment before the missing SSE assessments#	Yes	≥ 13 weeks between last SSE assessment and death
Neither SSE nor Death by database cutoff date	Last SSE assessment prior to database cutoff	Yes	Neither SSE nor death

*The earliest end date in the table is used in calculating the SSE-FS.

#: use randomization date instead of last SSE assessment date if no post-randomization SSE assessment.

Note: symptomatic skeletal events immediately after missing SSE assessments are still counted as events in the analysis of SSE-FS.

Comparison 2:

- All subjects eligible for Comparison 2, refer to [Table 9–2](#) for censoring rules.
- Symptomatic Skeletal Event Free Survival (SSE-FS) following Week 24 baseline= End Date – Date of Week 24 baseline(the 6th dose date) +1

Table 9–2 Comparison 2: Censoring for Symptomatic Skeletal Event Free Survival (SSE-FS)

Situation	End Date	Censored	Reason for Censoring
No SSE assessment or death following Week 24 baseline	Date of Week 24 baseline	Yes	No post-Week 24 baseline SSE assessments and no

			death.
Had an SSE event between date of randomization and Week 24 baseline	Date of Week 24 baseline	Yes	First event occurred between date of randomization and Week 24 baseline
Subject had a SSE event after Week 24 baseline	Date of first SSE	No*	N/A
Death without prior SSE (<13 weeks between last SSE assessment and death) #	Date of Death	No*	N/A
Death without prior SSE (≥ 13 weeks between last SSE assessment and death) #	Last SSE assessment before the missing SSE assessments#	Yes	≥ 13 weeks between last SSE assessment and death
Neither SSE nor Death by database cutoff date	Last SSE assessment prior to database cutoff	Yes	Neither SSE nor death

*The earliest end date in the table is used in calculating the SSE-FS.

#: use Week 24 baseline date instead of last SSE assessment date if no post-Week 24 baseline SSE assessment.

Note: symptomatic skeletal events immediately after missing SSE assessments are still counted as events in the analysis of SSE-FS.

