3.4 Determination of sample size

The sample size is based on two separate comparisons with no multiple-testing adjustment:

Comparison 1:

H01: $SSE-FS_{\text{high dose}} = SSE-FS_{\text{standard dose}}$, versus

HA1: $SSE-FS_{\text{high dose}} > SSE-FS_{\text{standard dose}}$.

This comparison will consider SSE-FS following randomization. Arm C subjects will be pooled with Arm A for the standard dose group. Refer to pooling algorithm in Section 4.5.2 and Censoring rules in Table 9–1.

Comparison 2:

H02: SSE-FS_{extended dose} = SSE-FS_{Standard dose}, versus

HA2: SSE-FS_{extended dose} > SSE-FS_{Standard dose}.

This comparison will include Arm A and Arm C subjects who received 6 or more doses.

The sample size calculations assume 30 subjects/month enrollment with 7 months ramp-up and a 3% loss to follow-up per month. The accrual period is anticipated to last approximately 16 months. Overall, 360 subjects are expected to be randomized at a 1:1:1 ratio. The primary endpoint cut-off, as defined in Section 3.3, is estimated to be reached in an average of 39.1 months.

- Comparison 1 assumes:
 - Arm A (standard dose) subjects have constant median SSE-FS of 9 months throughout the study
 - Arm C (extended dose) subjects have median SSE-FS of 9 months during the first 24 weeks of the study
 - Arm B (high dose) subjects have constant 50% improvement in SSE-FS (median 13.5, hazard ratio 0.667) .

Simulations indicated an average of 186.61 events would occur for this comparison at primary endpoint cut-off, and a 1-sided log-rank test with 0.10 significance gave approximately 90.5% power to test H01 versus HA1.

- Comparison 2 assumes:
 - Arm A (standard dose) subjects have constant median SSE-FS of 9 months
 - Arm C Extended dose subjects have
 - Median SSE-FS of 9 months for the first 24 weeks
 - A 65% improvement (median 14.85, hazard ratio 0.606) thereafter.

With 240 of 360 subjects randomized to Treatment Arm A and Treatment Arm C, simulations indicated that 44.65% of randomized subjects (107.2 of 240) would have a SSE-FS event or loss to follow-up during the first 24 weeks, leaving an estimated 55.35% (132.8) surviving SSE-free and eligible for inclusion at 24 weeks. An average of 74.91 simulated events occurred for this comparison, and a 1-sided log-rank test with 0.10 significance (0.2 for two-sided test) gave approximately 80.6% power to test H02 versus HA2.

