4.5 Data Rules

4.5.1 Determining Baseline Values

This study has two distinct baselines for efficacy analyses, the randomization baseline and the Week 24 baseline.

Randomization baseline value for efficacy parameters: is defined as the last non-missing value on or before the date of randomization.

Week 24 baseline: Unless otherwise specified, the ‘Week 24 baseline’ is defined as the date of the 6th injection. This baseline is defined only for those subjects who are eligible for Comparison 2 analyses. That is, subjects who had received at least 6 injections.

Week 24 baseline value for efficacy parameters: Unless otherwise specified, the ‘Week 24 baseline value’ is defined as the last non-missing value on or before the date of the 6th injection.

Ideally, this visit would be the date of the 7th injection for Arm C subjects and expected 7th injection date for Arm A subjects. However, the end of treatment visit (30±7 days from last dose) for Arm A subjects could be missing due to consent withdrawal or happen out of visit window. Hence, there is no comparable visit for Arm A subjects that could be used as the expected 7th injection date.

To account for this and achieve comparability between the two arms, the 6th injection date is used as the reference date for Comparison 2 subjects. It should be noted that this could lead to a somewhat dilution of the treatment effect in Arm C due to an early reference date.

Baseline value for safety parameters: is defined as the last non-missing value on or before the date of first dose.

4.5.2 Pooling cut-off date for Arm C subjects in Comparison 1

For Comparison 1, Arm C subjects are planned to be pooled with Arm A subjects. This pooling will be done such a way that only comparable data from Arm C subject pooled. The following algorithm will be used to identify the cut-off date for pooling:

Arm C: Pooling cut-off date = $7*28 + \text{randomization date}$; for subjects that were randomized but not treated,
= $(7-x)*28 + \text{last dose date}$; for $1 \leq x \leq 6$,
= 7th dose date; for $x \geq 7$,
where x be the number of injections received.

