6.2.1 Primary Efficacy Analysis

The primary efficacy endpoint, symptomatic skeletal event-free survival (SSE-FS), will be defined separately for each of the two efficacy evaluations described above, as follows:

For Comparison 1, SSE-FS following randomization is defined in ITT subjects as the time from randomization to an SSE or death, whichever occurs first. Refer to Appendix 9.1.1 for censoring rules.

For Comparison 2, SSE-FS from 6th dose is defined in W24 subjects as the time from Week 24 baseline (the 6th dose date) to an SSE or death, whichever occurs first. Refer to Appendix 9.1.1 for censoring rules.

For both evaluations, a symptomatic skeletal event (SSE) is defined as follows:

- The use of external beam radiotherapy (EBRT) to relieve skeletal symptoms
- The occurrence of new symptomatic pathological bone fractures (vertebral or non-vertebral)
- The occurrence of spinal cord compression
- A tumor related orthopedic surgical intervention.

The censoring rules for SSE-FS for each comparison are summarized in [Table 9–1](#) and [Table 9–2](#) of [Appendix 9.1.1](#). Stratified statistical tests described in this section refers to two of the three randomization strata as determined by the IXRS: use of prior chemotherapy (≤ 1 regimen versus > 1 regimen), and total ALP (< 220 U/L versus ≥ 220 U/L). Note that Average worst pain score (WPS) was included as one of stratification factor for randomization in order to balance the baseline pain across three arms. However, WPS will not be included in the analysis to avoid sparse cells due to relatively small sample size within each arm.

Each analysis will use a stratified log-rank test. A one-sided significance level of 0.10 will be used for interpretation of the results. Additionally, the hazard ratio (respectively high dose/standard dose and extended dose/standard dose) will be computed together with the two sided -80% and -95% CIs using a stratified Cox regression model. There will be no adjustment for multiple comparisons.

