9.1.3 Censoring rules for other time-to-event endpoints

Comparison 1:

- Arm C subjects who had relevant event assessment or event after ‘pooling cut-off date’ will be censored on last assessment date prior to ‘pooling cut-off date’. Refer to Section 4.5 for pooling cut-off date.
- All other subjects in arms A, B and C, refer to
- [Table 9–4](#) for censoring rules.
- Randomization baseline is used for this comparison
- Time-to-event following randomization = End date - date of randomization +1

Comparison 2:

- Subjects who had a relevant event between date of randomization and Week 24 baseline will be censored at date of Week 24 baseline, with the reason ‘First event occurred between date of randomization and Week 24 baseline’.
- All other subjects refer to
- [Table 9–4](#).
- Week 24 baseline is used for this comparison for following endpoints: Time to first SSE and Time to Pain progression
- Randomization baseline is used for this comparison for exploratory endpoints :Time to ALP progression, time to PSA progression, time to increase in analgesic use and time to pain progression or increase in analgesic use.
- The assessment prior to treatment start is used as baseline for time to increase in physical symptoms of disease.
- Time-to-event following Week 24 baseline = End date - date of week 24 baseline +1.

[Table 9–4](#) applies to the following endpoints:

- **Time to First Symptomatic Skeletal Event**
- **Time to Pain Progression**
- **Time to ALP Progression**
- **Time to ALP Progression without 12-week Restriction**
- **Time to PSA Progression**
- **Time to PSA Progression without 12-week Restriction**
- **Time to Increase in Analgesic Use**
 - Requires Baseline WPS ≤ 7 for inclusion in analysis
- **Time to Pain progression or increase in analgesic use**
 - Requires Baseline WPS ≤ 7 for inclusion in analysis
 - The last assessment for censoring purposes refers to the latest date Pain Progression assessment. The earlier of the date of pain progression or increase in analgesic use is taken as the endpoint.
- **Time to increase in physical symptoms of disease following start of treatment based on FPSI-DRS-P**

Table 9–4 Time-to Event Censoring Rules

Situation	End Date	Censored	Reason for Censoring
No baseline assessment	Relevant Baseline Date	Yes	No baseline assessment.
No post baseline assessment	Relevant Baseline Date	Yes	No post-baseline assessment.
Subject had an event	Date of first event	No	N/A

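### In Comparison 1 the Arm C censoring bullet omits the condition that no event had occurred by the pooling cut-off; programmed literally, it would discard early standard-dose events

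*SAP*

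**What the plan says.** For Comparison 1, Arm C is pooled with Arm A as the standard-dose group, and section 4.5.2 sets a pooling cut-off date for each Arm C subject. For a subject with seven or more injections this is the date of the 7th dose.

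Section 9.1.1 then gives two bullets for SSE-FS:

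- The first covers "Arm C subjects who had SSE assessments or SSE event or death (in the absence of an SSE event) after" the pooling cut-off date. These subjects are censored at the last SSE assessment before that date.
- The second reads "All other subjects in arms A, B and C, refer to" Table 9–1. That table counts a first SSE as an event on its date, and its footnote says "The earliest end date in the table is used in calculating the SSE-FS".

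Section 9.1.3 uses the same structure for the other time-to-event endpoints: "Arm C subjects who had relevant event assessment or event after" the cut-off leads to censoring at the last earlier assessment.

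Three other places bear on how these bullets should work:

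- Section 6.2.1: "SSE-FS following randomization is defined in ITT subjects as the time from randomization to an SSE or death, whichever occurs first".
- Section 4.5.2: pooling is to be done so that "only comparable data from Arm C subject pooled".
- Section 3.4: the Comparison 1 power simulation takes Arm C to have a 9-month median SSE-FS over the first 24 weeks.

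The two supplemental SAPs refer back to the main SAP for efficacy and do not alter these rules.

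**The concern.** The first bullet has three alternative triggers: an SSE assessment, an SSE, or a death after the cut-off. The bracket about absence of an SSE qualifies death only. One SSE assessment after the cut-off is therefore enough to trigger censoring, whatever happened before. The second bullet sends only the remaining subjects to Table 9–1, so neither the table's first-SSE row nor its earliest-date footnote reaches a man already caught by the first bullet.

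Take an Arm C man with an SSE at Week 10 who is assessed again at Week 30. Read literally, he is censored at his last assessment before about Week 24, and the Week 10 event is not counted.

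This can affect only Arm C, so the loss falls wholly on the standard-dose side of a co-primary comparison. It would understate the standard-dose hazard and bias the estimate, as well as cost precision. Under 9.1.3 the same applies to time to first SSE, a secondary endpoint that is formally tested, and to the pain, PSA, ALP and analgesic endpoints.

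**Working it through.** **1. Can such subjects exist?** Table 9–2 has a row for a subject who "Had an SSE event between date of randomization and Week 24 baseline". The Week 24 baseline requires six injections (4.5.1), so a man can have an early SSE and still reach the 6th dose. The SAP does not say how often SSEs are assessed after a first one.

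**2. Inputs, all from section 3.4 unless stated.** 360 subjects at 1:1:1 (120 per arm); accrual of 30 per month with a 7-month ramp-up; 3% monthly loss; median 9 months in Arm A, and in Arm C up to Week 24; hazard ratio 0.667 for Arm B; hazard ratio 0.606 for Arm C after Week 24; last treatment 44 weeks after the last accrual; cut-off at the latest of 135 Comparison 1 events, 75 Comparison 2 events and 30 days after last treatment (3.3).

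**3. The plan's own figure.** The SAP expects 186.61 events, and "a 1-sided log-rank test with 0.10 significance gave approximately 90.5% power to test H01 versus HA1".

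- Schoenfeld formula with one third of subjects in Arm B: power = Φ(√(D·p·(1−p))·|ln HR| − z₀.₉₀) = Φ(√(186.61 × 1/3 × 2/3) × 0.405 − 1.282) = Φ(6.44 × 0.405 − 1.282) ≈ 90.8%.
- Simulation of 10,000 trials (exponential times, unstratified log-rank test), keeping Arm C events up to Week 24: 185.9 events, power 90.8%, cut-off at 39.7 months (SAP: 39.1). For Comparison 2: 74.7 events (SAP: 74.91) and power 79.9% (SAP: 80.6%).

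The stated design is thus reproduced when early Arm C events count.

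**4. Arm C events before Week 24.** Event rate λ = ln 2 / 9 = 0.0770 per month; loss rate μ = −ln 0.97 = 0.0305; Week 24 = 168 / 30.4375 = 5.52 months.

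- Event or loss by Week 24: 1 − exp(−(0.0770 + 0.0305) × 5.52) = 44.7% (SAP: 44.65%).
- Events: 120 × 0.447 × 0.0770 / 0.1075 ≈ 38.5 (simulation: 38.4), about 21% of the 186 events in Comparison 1.

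**5. Effect of literal programming.** Only early events that are SSEs followed by a later assessment or SSE are lost. The SAP does not give that share, so a range is assumed. Affected subjects were censored at Week 24, as an approximation to the last assessment before the cut-off.

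| Assumed share | Events lost | Events left | Mean HR (true 0.667) | Power | Mean HR, no true effect | One-sided rejection, no true effect |
|---|---|---|---|---|---|---|
| 0% | 0 | 185.9 | 0.67 | 91% | 1.00 | 10.4% |
| 25% | 9.6 | 176.3 | 0.72 | 78% | 1.10 | 2.9% |
| 50% | 19.2 | 166.7 | 0.78 | 58% | 1.21 | 0.7% |
| 75% | 28.7 | 157.2 | 0.86 | 36% | 1.34 | 0.1% |
| 100% (upper bound) | 38.4 | 147.5 | 0.94 | 17% | 1.50 | 0.02% |

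**The case against.** The strongest reply is that the SAP read as a whole does not ask for early events to be discarded. The definition in 6.2.1 is complete at the first SSE. Section 4.5.2 wants comparable Arm C data, and data before the cut-off are comparable. The reason given in the radiological tables (9.1.4 and 9.1.5) refers only to Arm C events after Week 24. The overall survival bullet in 9.1.2 has the same form and does no harm, because nobody who died before the cut-off can meet it. The SSE bullet looks like that template carried over to a non-fatal event without the extra condition it then needs. This stands: the intent was almost certainly to drop only later events, and a careful programmer might do so.

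Several stronger readings are tempting, and the document does not support them:

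- *That standard-dose events will be deleted, or that the sponsor chose this.* The bullet says so only if taken alone, and it conflicts with other sections.
- *That power will fall to a particular figure.* The share of early events that are SSEs with later assessment is not in the SAP. Table 9–2 shows that men may continue to the 6th dose after an SSE, not that further SSE assessments are recorded.
- *That the 135-event trigger is compromised.* The SAP expects 186.61 events at the cut-off, so 135 is not the binding criterion. Even the upper bound leaves about 148.
- *That false positives rise.* The bias works against the high dose, and the one-sided rejection rate falls below 10%.

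Deaths before the cut-off are unaffected. So is the planned comparison of Arm A with Arm B alone (6.2), with about 148 events and 87% power on the same inputs, but that is a sensitivity analysis. In 9.1.3, time to pain progression is not on the list for hypothesis testing, and PSA and ALP are exploratory.

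The reply does not remove the need for a correction. Section 9.1.1 is the operative derivation rule for a co-primary endpoint. Following it literally contradicts 6.2.1, while following 6.2.1 departs from it. Two programmers could each defend a different event count.

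**Conclusion.** The point holds as a drafting error in a binding rule. The Arm C bullets in 9.1.1 and 9.1.3 omit the condition that no event occurred on or before the pooling cut-off, and in that form they conflict with 6.2.1, 4.5.2 and 3.4.

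The direction of the error under literal programming is certain: events leave only the pooled standard-dose group, and the high/standard hazard ratio moves upward. Its size is not certain. The figure of about 38 Arm C events before Week 24 follows from the SAP's inputs. The effects on the hazard ratio and power are illustrations that depend on the assumed 25% to 75% share, on exponential times and on an unstratified test. Analysis timing is not materially affected.

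**What to change.** - In 9.1.1, limit the first Comparison 1 bullet to Arm C subjects with no SSE and no death on or before the pooling cut-off date, and send all others to Table 9–1.
- In 9.1.3, limit the parallel bullet to Arm C subjects with no relevant event on or before that date, and send all others to Table 9–4.
- In both places, add that a first event on or before the pooling cut-off date counts as an event on its own date, whatever is observed later.

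This is a change of SAP wording only, plus a check that any derivation program already written follows it. It needs no new data and no change to the sample size, and it restores the rule under which the stated 186.61 events and 90.5% power are reproduced.

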9.1.2 Censoring rules for Overall Survival (OS)

Comparison 1:

- Arm C subjects who have died or are known to be alive after ‘pooling cut-off date’ will be censored on the ‘pooling cut-off’ date. Refer to Section 4.5 for pooling cut-off date.
- All other subjects in arms A, B and C, refer to [Table 9–3](#) for censoring rules.
- Overall Survival (OS) following randomization = End Date – Date of Randomization +1

Comparison 2

- For Comparison 2 eligible subjects, refer to [Table 9-3](#) for censoring rules.
- Overall Survival (OS) following Week 24 baseline = End Date – Date of Week 24 baseline(the 6th dose date) +1

Table 9–3 Overall Survival censoring rules

Situation	End Date	Censored	Reason for Censoring
Death on or prior to database cut off date	Date of Death	No	N/A
Not known to have died as of database cut off date	Last known alive date (LKAD) on or prior to database cutoff	Yes	No Death
Lost to follow-up prior to database cutoff	Last known alive date (LKAD)	Yes	Lost to follow up

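### Comparison 1 censors event-free Arm C subjects at the last SSE assessment before the pooling cut-off but keeps Arm C events up to the cut-off, which biases the co-primary test towards high dose

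*SAP*

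**What the plan says.** SAP section 4.5.2 sets the pooling cut-off for Arm C. It is the 7th-dose date for subjects with seven or more doses, and a projected date for those who stopped earlier or were never treated.

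Section 9.1.1 then applies the cut-off to SSE-FS. It covers "Arm C subjects who had SSE assessments or SSE event or death (in the absence of an SSE event) after" the cut-off; such a subject "will be censored on last SSE assessment date prior to" it. All remaining subjects follow Table 9-1, where an SSE counts on its own date. A death also counts on its own date if it falls less than 13 weeks after the last SSE assessment.

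The same situation is handled differently elsewhere:
- OS (section 9.1.2): "Arm C subjects who have died or are known to be alive after" the cut-off are censored on the cut-off date itself.
- rPFS (section 9.1.5): censoring is at the last radiological assessment on or before the cut-off.
- Other time-to-event endpoints, including time to first SSE (section 9.1.3): the trigger is "Arm C subjects who had relevant event assessment or event after" the cut-off, with censoring at the last assessment before it, as for SSE-FS.

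Section 6.2 plans an Arm A versus Arm B repeat of the Comparison 1 analyses, without Arm C, as a sensitivity analysis.

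**The concern.** A subject assessed, or having a first SSE, after the cut-off is known to have been event-free at the cut-off. The rule nevertheless takes that subject out of the risk set at an earlier visit. A subject with an SSE or death in the same interval stays in and counts as an event. Whether follow-up in the interval is used therefore depends on the outcome, which is informative censoring.

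Only Arm C is truncated in this way, and Arm C sits entirely in the standard-dose group. The standard-dose hazard is overstated, so high dose looks better than it is in a co-primary test. The design simulation in section 3.4 assumed continuous event and censoring times, so its operating characteristics do not cover this rule.

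**Working it through.** **Inputs** (SAP section 3.4 unless stated)
- "Arm A (standard dose) subjects have constant median SSE-FS of 9 months throughout the study": hazard ln 2 / 9 = 0.0770 per month.
- "Arm C (extended dose) subjects have median SSE-FS of 9 months during the first 24 weeks of the study".
- High dose HR 0.667; 120 subjects per arm; 3% loss per month; one-sided 0.10.
- 132.8 of 240 Arm A and C subjects event-free and in follow-up at 24 weeks (55.35%), so 132.8 / 2 = 66.4 in Arm C.
- 44 weeks = 10.12 months, so 1 week = 0.23 months.
- Gap from last SSE assessment to cut-off: **assumption**, not in the SAP. The range is 0 to 4 weeks. Four weeks is the dosing interval (section 1), and applies if SSE status is recorded at injection visits and the 7th-dose day is not before itself.

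**Step 1: reproduce the plan.** The SAP gives a mean Comparison 1 event count of 186.61. For power it states that "a 1-sided log-rank test with 0.10 significance gave approximately 90.5% power to test H01 versus HA1". The Schoenfeld formula with 1:2 allocation gives ln(1.5) × √(186.61 × 1/3 × 2/3) − 1.28 = 0.405 × 6.44 − 1.28 = 1.33, a power of 90.8%. Simulation with Arm C censored exactly at 24 weeks (10,000 replicates) gives 186.1 events and 90.7% power. The design is reproduced.

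**Step 2: what the rule removes.** With a 4-week gap, 66.4 × 4 × 0.23 = 61 person-months of event-free Arm C follow-up are dropped. All of the roughly 38.5 Arm C events before the cut-off are kept.

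**Step 3: hand check of the null HR, 4-week gap (weeks 20-24).**
- Exit rate from the risk set: −ln(0.5535) / 24 = 0.0246 per week. At week 22, 120 × exp(−22 × 0.0246) ≈ 69.8 per arm.
- Events per arm in the window: 69.8 × 0.92 × 0.0770 = 4.94; over three arms, 14.8.
- In the window the standard-dose group has events from two arms but time at risk from one, so the apparent HR there is about 0.5.
- The simulated null total is 190.6 events, so the window holds 14.8 / 190.6 = 7.8% of them. Weighting by events, ln HR ≈ 0.078 × ln 0.5 = −0.054, so HR ≈ 0.95.

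**Step 4: hand check of the error rate.** The shift in the test statistic is ln(0.95) × √(190.6 × 2/9) = −0.0513 × 6.51 = −0.33. The error is Φ(−1.28 + 0.33) ≈ 17%.

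**Step 5: simulation under the null** (20,000 replicates, unstratified log-rank, nominal 10%)

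| Gap | One-sided error | Mean HR |
|---|---|---|
| 0 (censor at cut-off) | 9.7% | 1.00 |
| Uniform 0-4 weeks | 12.5% | 0.978 |
| 4 weeks | 16.8% | 0.950 |

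A second simulation gave 9.5%, 13.0% and 17.7%. A third, with analysis fixed at the SAP's 39.1 months, gave 10.1% with no gap and 17.4% with 4 weeks.

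**Step 6: under the planned effect.** Censoring at the cut-off gives HR 0.665 and 90.7% power. With a 4-week gap the HR is 0.634 and the rejection rate 94.8%. The extra rejections come from bias, not information.

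**Step 7: is it just last-assessment censoring?** Arms A and B were also censored at their last assessment (4-weekly to Week 24, then 12-weekly, assumed). The error stays at 16.7% (HR 0.950). With that same censoring but Arm C censored at the cut-off, it returns to 9.7%.

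**The case against.** The strongest reply is that the size cannot be read from the SAP. The visit schedule is left to the protocol, and if an assessment on the 7th-dose day were counted, the gap and the bias would be zero for subjects dosed on schedule. This stands as a limit on the size. It does not rescue the text, which calls for an assessment before the cut-off, whereas the rPFS rule says on or before.

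A second reply is that last-assessment censoring is usual and applies to every arm. For Arms A and B, event-free subjects are censored this way relative to the database cut-off, and Step 7 shows that adding it there does not remove the effect.

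A third is that Arm A versus Arm B is already planned. That analysis is free of this bias (simulated error 10.0%, power 88.0%) and would help expose a result produced by pooling. It remains a sensitivity analysis beside a biased co-primary test.

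Two stronger readings are tempting:
- A reader might take 17% as the trial's actual error rate. It is the result under an assumed 4-week gap. Gaps longer than 4 weeks would bias more, but the SAP gives no basis for them in subjects dosed on schedule.
- A reader might take the section 9.1.1 trigger literally, so that an Arm C subject with an SSE before the cut-off who is merely assessed after it is censored and the event lost. That would push the other way and cost power. The Table 9-1 footnote that the earliest end date is used suggests this is not meant, and the OS bullet is worded just as loosely. Nothing in the SAP says how many subjects would be affected, so no size can be claimed. The wording should still be closed, because only the remaining subjects are sent to Table 9-1.

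**Conclusion.** The concern holds. On the natural reading, in which Arm C events before the cut-off are kept, section 9.1.1 makes censoring depend on outcome in the standard-dose group alone and favours high dose in a co-primary test. The direction follows from the rule for any non-zero gap. The size depends on the unstated assessment interval: error of about 12.5-13% for a gap uniform over 0-4 weeks, and about 17% for 4 weeks, against a nominal 10%. At 4 weeks the planned HR of 0.667 is estimated as about 0.64. These figures assume the section 3.4 hazards, dosing on schedule and an unstratified test. The loose trigger wording is a separate matter of clarification.

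**What to change.** For SSE-FS and time to first SSE in Comparison 1:
1. First apply Table 9-1 (or Table 9-4) to Arm C data up to the pooling cut-off, including the rule for deaths 13 or more weeks after the last SSE assessment. For SSE-FS, an SSE or qualifying death on or before the cut-off is an event on its own date, whatever is recorded later; for time to first SSE, this applies to an SSE.
2. Censor on the pooling cut-off date those Arm C subjects with no such event whose event-free status at the cut-off is established by a later SSE assessment, a later SSE, or a later death within 13 weeks of the last SSE assessment. This matches the OS rule.
3. Censor other Arm C subjects as Table 9-1 (or Table 9-4) provides.

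Keeping the 13-week rule matters: without it, late deaths would count as events in Arm C but be censored in Arms A and B, a new imbalance in the same direction. In section 9.1.3, add to the trigger the condition that no event occurred on or before the pooling cut-off.

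The cost is one derivation change and a few sentences, with no new data. The downside for the sponsor is a slightly less favourable estimate for high dose.
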